#### 4.5 Data distribution and model checking

Analysis of covariance (ANCOVA) will be used to compare continuous data between the intervention and control group. For the primary outcome, SMART risk score at 6 months is considered the dependent variable, and the categorical grouping variable (intervention or control) will be added as independent variable. As covariates, the SMART risk score at baseline and hospital will be added. The ANCOVA model will be implemented using the `lm` function in R. Assumptions of homogeneity of regression slopes and homogeneity of variances will be checked with the imputed data sets.

For comparison of changes in LDL, body weight, CRP and systolic blood pressure, similar ANCOVAs will be performed with adjustment for study site and baseline values.

Chi-Square tests will be used for the analysis of medication use as this is presented as dichotomous data. The 95% CI will be presented for the difference in proportions. If expected cell frequencies are less than 5, Fisher's exact tests will be used.

If the assumptions underlying ANCOVA (normal distribution of residuals, homogeneity of variances) are not satisfied, data will be transformed. If data is still not normally distributed, linear mixed models will be used. This model will include fixed effects for the SMART risk score, and a random intercept for the grouping variable to account for individual variability within each group. The models will be implemented using the '`lme4`' package in R.

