## 2.4 Design

The Voed je Beter trial is a multicenter, randomized, controlled trial with two parallel arms. Patients were randomly assigned in a 1:1 ratio to usual care or the intervention group. The allocation sequence was computer-generated using block-randomization with variable block sizes (4, 6, 8). Allocation was stratified by hospital.

The intervention period was set at six months. Patients in the intervention group were referred to a dietitian close to their home address or, if that was not available, an online dietitian practice. Patients met with the dietitian seven times within six months with a maximum of 5 clock hours in total. Dietitians were instructed to guide the patients in improving adherence to the Dutch Dietary Guidelines (11). The Dutch Dietary Guidelines include recommendations on 16 components, including salt, vegetables, fruit, whole grain products, legumes, nuts, dairy, fish, tea, fats and oils, coffee, red meat, processed meat, sweetened beverages and fruit juices, and alcohol. Together with the dietitian, patients chose themselves which components they were going to improve. The diet in the study was therefore not prescriptive; goals were negotiated individually with each participant during their first session with the dietitian and were reviewed at each visit. Dietitians were instructed to at least set a goal on improving the intake of salt, fruit or vegetables as these are hypothesized to be the most relevant components for patients with cardiovascular diseases. Due to the nature of the intervention, blinding of dietitians, researchers, and patients was not possible. To limit bias during data analysis, an independent researcher will recode the groups in a way it is no longer possible to determine which group is intervention and which is control. The unblinding of the groups will take place after analyzing the primary outcome.

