## 2.7 Primary endpoints

The primary outcome of this study is change in 10-year CVD risk as predicted with the SMART risk score (10). The SMART risk score is a model to estimate 10-year recurrent cardiovascular risk expressed as percentage and to predict the effect of treatments such as smoking cessation, blood pressure lowering or lowering LDL-cholesterol (10). To assess the SMART risk score at baseline, we will use the model as shown in figure 1 below and described in (10). The model considers age (y), time since last cardiovascular event (y), type of CVD, having diabetes (y/n) smoking status (y/n), total cholesterol (mmol/l), high-density lipoprotein cholesterol (mmol/l), low-density lipoprotein cholesterol (mmol/l), triglycerides (mmol/l), C-reactive protein (CRP, mg/L), systolic blood pressure (mmHg), estimated Glomerular Filtration rate (eGFR) and anticoagulant (ATC code B01) use to estimate the 10-year recurrent cardiovascular risk. For type of CVD, the original formula includes factors for four different CVDs (coronary artery disease, cerebrovascular disease, aortic aneurysm and peripheral artery disease). For other CVDs, a factor representing the average of the factors associated with these four diseases is used.

*Figure 1 Calculation of 10-year CVD risk according to the SMART risk score*

10-year CVD risk (%) =  $(1 - 0.81066^{\exp(\text{linear predictor} + 2.099)}) \times 100\%$

In which Linear predictor =

```
-0.0349602236 * age +  
0.0005510715 * age^2 +  
ifelse(sex=="M", 0.2876587433, 0) +  
0.3455832714 * isSmoking +  
0.0018913154 * sbp +  
0.3181706587 * diabetesDiagnosis +  
0.2947019539 * coronaryArteryDisease +  
0.3483178604 * cerebrovascularDisease +  
0.3303566308 * aorticAneurysm +  
0.2244665798 * peripheralArteryDisease +  
0.2994607562 * otherDisease +  
0.0476995851 * yearsSinceFirstDiagnosis -  
0.0016497342 * yearsSinceFirstDiagnosis^2 +  
0.5403642493 * log(nonHdl) -
```

0.0396752081 * egfr +
0.0002186126 * egfr^2 +
0.1517601731 * log(crp) -
0.2107210313 * usingAnticoag

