To estimate the change in 10-year risk during the 6 months of the study, we will consider changes in LDL cholesterol and systolic blood pressure as these are causal risk factors known to be influenced by diet (16, 17). With the SMART risk model, the effect of changes in these risk factor can be estimated by using a Hazard Ratio (HR) related to these risk factors (10). Every decrease of 1.0 mmol/L in LDL-cholesterol is shown to reduce an individual's cardiovascular risk with 20%, corresponding to an HR of 0.80 (18). Per decrease of 10 mmHg for systolic blood pressure, cardiovascular risk is estimated to be reduced with 22%, hence a HR of 0.78 is used (19). Multiplying the effects of the changes in LDL-cholesterol and systolic blood pressure with the baseline risk, gives us the predicted change in 10-year risk at the end of the intervention.

In short, 10-year CVD risk at six months is calculated as  $10\text{-year CVD risk at baseline} * (0.78^{\text{LDL-c end} - \text{LDL-c baseline}}) * (0.8^{(\text{SBP end} - \text{SBP baseline})/10})$ . By subtracting the 10-year CVD risk at six months from the 10-year CVD risk at baseline, the change in SMART risk score will be calculated.

*Table 1 Example calculation of 10-year CVD risk at six months using changes in LDL-cholesterol and systolic blood pressure*

Baseline risk	Change in LDL-c	Change in SBP	6 months risk	Change in risk
1%	increased with 1mmol/l	increased with 3 mmHg	$1 * (0.78^{-1}) * (0.8^{3/10}) = 1.2\%$	+0.2%
20%	decreased with 1mmol/l	decreased with 5 mmHg	$20 * (0.78^1) * (0.8^{5/10}) = 13.9\%$	-6.1%
20%	decreased with 0.5 mmol/l	decreased with 2 mmHg	$20 * (0.78^{0.5}) * (0.8^{2/10}) = 17.3\%$	-2.7%
80%	no change	increased with 1 mmHg	$80 * (0.78^0) * (0.8^{1/10}) = 80.9\%$	+0.9%

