## 2.9 Sample size calculation

The study was powered to detect a difference in estimated 10-year CVD risk between the intervention and control group at 6 months of 3.3% (20), with an assumed standard deviation of 6.3% (21). Based on those numbers, a sample size of 114 patients (57 patients per group) was needed to provide a

power of 80% with an alpha 0.05. Considering a possible 20% dropouts, the required sample was increased to 144 patients.

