### 4.4 Missing data

Researchers were instructed to obtain complete CRFs, but participants dropping out of the study resulted in missing data. Data is assumed to be missing at random (MAR). Missing data necessary for the calculation of the primary outcome will be imputed by chained equations with the MICE package for R software ( $m=10$  imputations, iterations =10) (22). In more detail, with this method missing values are imputed by using a model that incorporates random variation. Every variable (except for personID) in the dataset is considered a potential predictor for imputing missing values in other variables.

For the imputation, ten datasets will be created and the data analysis will be performed on these ten datasets. After performing the data-analysis on the ten datasets containing the imputed data, the ten coefficients are estimated by the imputed dataset into one final regression coefficient. The variance will be estimated using the pool() function. To obtain the final coefficients we take the mean of the ten values. We calculate the variance of the estimated coefficient by factoring in the within (accounting

for differences in predicted values from the dataset regarding each observation) and between (accounting for differences between ten datasets) imputation variance. If convergence is not achieved after 10 iterations, more iterations will be used to improve convergence.

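### The primary ANCOVA is valid but leaves out baseline systolic pressure and LDL, whose changes drive the six-month score, and so gives up some precision

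*SAP*

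**What the plan says.** Section 4.5 of the SAP fixes the primary model. The outcome is set by "SMART risk score at 6 months is considered the dependent variable", group is the factor of interest, and the adjustment is: "As covariates, the SMART risk score at baseline and hospital will be added". The secondary ANCOVAs for systolic pressure and LDL in the same section each adjust for site and the variable's own baseline.

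Section 2.7 does not obtain six-month risk by running the SMART equation again. It obtains it by "Multiplying the effects of the changes in LDL-cholesterol and systolic blood pressure with the baseline risk", with a hazard ratio of 0.80 per 1 mmol/L fall in LDL and 0.78 per 10 mmHg fall in systolic pressure. In the baseline equation (Figure 1 of that section) systolic pressure enters as "0.0018913154 * sbp". LDL has no term of its own; lipids enter as the log of non-HDL cholesterol, with coefficient 0.540.

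**The concern.** Adjusting for the baseline of the outcome normally deals with regression to the mean. Here it does so only in part, because the baseline score and the change rule weight the same measurements differently. A patient with a high systolic reading at baseline will tend to show a fall at six months whatever the arm. The outcome moves strongly with that fall, yet baseline SMART risk barely registers that the starting value was high. The same applies, less sharply, to LDL. This predictable variation stays in the residual and widens the primary confidence interval.

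Randomisation keeps the estimate unbiased. The inaccuracy that arises when baseline pressure or LDL is imbalanced by chance is the same loss seen from another side and should not be counted twice. Precision matters here because section 2.9 planned for 144 patients, while the Table 1 shell in section 5 shows a total of 124.

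**Working it through.** **The plan's own figure.** Section 2.9 gives a difference of 3.3 points, SD 6.3, two-sided 5% and 80% power. n per arm = 2 × (1.96 + 0.84)² × 6.3² / 3.3² = 57.2. The stated 57 per arm gives 79.9% power, so the calculation reproduces as a two-group comparison.

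**What baseline risk carries.**

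- Systolic pressure: the change rule implies −ln(0.78)/10 = 0.0248 per mmHg. The score uses 0.00189. Ratio 0.0248/0.00189 = 13.1. Ten mmHg multiplies the baseline hazard by exp(0.0189) = 1.019, but moves six-month risk by 1/0.78 = 1.28.
- LDL: if 1 mmol/L takes non-HDL from 2.95 to 3.95 (assumed values), the baseline hazard changes by (3.95/2.95)^0.540 = 1.17, against 1/0.80 = 1.25 in the change rule. That is ln 1.17 / ln 1.25, about 70% of the weight on the log scale.
- Simulated correlation of baseline risk was 0.04–0.08 with systolic pressure and 0.19–0.32 with LDL, since age, eGFR, CRP and the other inputs dominate the score.

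**How large the gain can be.** For a measurement with equal variances and baseline-to-follow-up correlation r, the change has variance 2σ²(1−r). After adjustment for its baseline, σ²(1−r²) remains. The ratio is (1+r)/2: 0.70 at r = 0.4 and 0.90 at r = 0.8. This is a simplified guide, because the actual outcome is a product with baseline risk.

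**Simulation.** Assumed inputs, none given in the SAP: N=124, systolic SD 17, LDL SD 0.75, mean risk 19–21% with SD 7 or 13 points, effects of −4 mmHg and −0.25 mmol/L. The hazard ratios are those in the text of section 2.7. Both models contain arm, hospital and baseline risk; the extended one adds baseline systolic pressure and LDL. There were 4,000 trials per cell. The interval column is 1 − √(1 − cut).

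| Correlation | Variance cut | Interval narrower by | Power gain (points) |
|---|---|---|---|
| 0.4 | 18–23% | 9–12% | 5–9 |
| 0.5 | 17–18% | 9% | 4–7 |
| 0.6 | 12–15% | 6–8% | 4–7 |
| 0.7 | 8–11% | 4–6% | 4–5 |
| 0.8 | 5–7% | 3–4% | 1–3 |
| 0.85 | 4–6% | 2–3% | 1–3 |

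Type I error was 4.3–5.3% for the planned model and 4.6–5.3% for the extended one.

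**Sensitivity.** A second simulation (systolic SD 18, LDL SD 0.8, mean risk 19–27%, systolic/LDL correlations from 0.4/0.5 to 0.8/0.9) gave residual-variance cuts of 7–21%, and about 14% at 0.6/0.7. At 0.6/0.7, with effects of −5 mmHg and −0.2 mmol/L, both models estimated −3.76 points; the empirical standard error was 2.01 against 1.87, and power 46% against 53%. Further runs used the hazard ratios as placed in the printed six-month formula, that formula's printed sign, mean risk near 72%, N=99, and SDs of 13 and 0.6. The cuts were 16–20% at 0.5, 8–12% at 0.7 and 3–7% at 0.85. The result therefore does not depend on how the printed formula is resolved or on the risk level.

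**Planning scale.** If 6.3 is read as the residual SD of the planned model, power is Φ(2.80/√(1 − cut) − 1.96): 82.0%, 84.0% or 87.6% for a cut of 5%, 10% or 19%.

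**The case against.** The best defence is that the planned model is the standard one: baseline value of the same score plus the stratification factor, valid under randomisation. Which further prognostic variables to include is then a matter of preference. That it is valid stands. The standard form, however, relies on the baseline score capturing regression to the mean in the outcome, and the construction in section 2.7 breaks that link.

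Four further points deserve weight.

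- The gain depends on correlations that the SAP does not give, and is small above about 0.7. This stands; only the direction is secure, for any correlation below 1.
- The contrast in weights is stark only for systolic pressure, since LDL keeps about 70% of its weight through non-HDL. This stands too, though LDL still shares little variance with baseline risk.
- The planning-scale power figures need 6.3 to be the ANCOVA residual SD, which section 2.9 does not say. They are illustrative.
- The imputation in section 4.4 already uses these baselines as predictors. With 20% missing completely at random and ten imputations, the cut fell from 19% to 17% at correlation 0.5, from 15% to 12.5% at 0.6 and from 10% to 9% at 0.7, and stayed at 7% at 0.8. The gain is trimmed but not removed.

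It can also be said that changing a valid primary model with data in hand needs justification. The justification here is structural and owes nothing to the results, but it holds only if the change precedes the analysis.

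**Conclusion.** The concern holds as a point of efficiency. The planned ANCOVA is unbiased over randomisation, keeps its type I error and contradicts nothing else in the SAP. It leaves unused two baseline measurements that predict the outcome and that baseline SMART risk carries weakly (LDL) or hardly at all (systolic pressure). Under the assumed SDs, patient mix and correlations of 0.4–0.85, the variance penalty runs from about 4% to 23%: moderate up to a correlation of about 0.7, small beyond it. The change is worth making because it costs so little, but the trial's validity does not depend on it.

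**What to change.** Amend the covariate sentence in section 4.5 so that the primary model adjusts for four baseline items: *SMART risk score, systolic blood pressure, LDL-cholesterol and hospital*. Carry the same list into any fallback model that section 4.5 retains.

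The amendment should be documented and dated before the primary model is first fitted to the recoded groups. Section 2.4 says "The unblinding of the groups will take place after analyzing the primary outcome". Recoding hides which arm is which but not the size of the difference between them, so the date that matters is the first fit, not the unblinding.

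The cost is one amendment and two degrees of freedom out of about 120. No patient is lost: baseline systolic pressure and LDL are needed to compute the outcome, and section 4.4 provides that "Missing data necessary for the calculation of the primary outcome will be imputed by chained equations".

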## 2.8 Secondary endpoints

As secondary outcomes, changes in LDL-cholesterol, body weight, CRP and systolic blood pressure will be presented and compared between groups. Similarly, the change in proportion of individuals using lipid lowering agents, antiplatelet or anticoagulant agents, or blood pressure lowering agents will be presented and compared between groups.

Changes in diet quality, as assessed with the Dutch Healthy Diet index, will be presented for the total population and for the two groups separately but will not be compared with statistical tests. Changes in smoking habits will be presented for the total population and for the two groups separately as % of individuals smoking at baseline and at 6 months.

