## 4. Statistical analysis

### 4.1 Significance

All statistical tests will use a significance level of  $\alpha=0.05$ . Two-tailed tests will be performed for all analyses involving statistical testing. Confidence intervals will be presented with a 95% degree of confidence.

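### Section 4.5 leaves the scale for CRP to an unnamed transformation chosen after a residual check, and the fallback behind it is a model for the SMART risk score that cannot give the planned CRP comparison

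*SAP*

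**What the plan says.** - **Status of CRP.** Section 2.8 makes it a tested secondary outcome: "changes in LDL-cholesterol, body weight, CRP and systolic blood pressure will be presented and compared between groups". Section 4.1 sets the test as two-sided at 0.05: "Two-tailed tests will be performed for all analyses involving statistical testing".
- **First-line model.** Section 4.5: "For comparison of changes in LDL, body weight, CRP and systolic blood pressure, similar ANCOVAs will be performed", adjusted for study site and the baseline value. No log scale is named.
- **Scale used elsewhere.** The risk equation in Figure 1 of section 2.7 enters CRP through the term "0.1517601731 * log(crp". Systolic blood pressure enters the same equation linearly.
- **Repair rule.** If residual normality or equal variances fail, section 4.5 has the data transformed. If they are still not normal, it moves to linear mixed models. The transformation, the check and its threshold are not given.
- **Fallback model.** "This model will include fixed effects for the SMART risk score", together with a random intercept for the grouping variable. No version is written for CRP or any other secondary outcome.
- **Reporting.** The Table 2 shell has a mean-difference column and no row for CRP.

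**The concern.** CRP is usually strongly right-skewed, and the log term in Figure 1 means the plan already handles it on that scale as a predictor. Starting the CRP outcome on the mg/L scale has three consequences.

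1. The first-line CRP model is almost certain to fail the residual check, so it is written to be replaced.
2. The replacement is chosen after the data are seen. What is reported, a difference in mg/L or a ratio of geometric means, therefore depends on an unrecorded decision.
3. If the chosen transformation also fails, the rule leads to a model that cannot answer the question. Group as a random intercept yields a variance component and no treatment contrast with a confidence interval. The only covariate named is the SMART risk score, so baseline CRP and hospital both drop out.

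At stake are the sensitivity of the CRP comparison and its freedom from post hoc choice, and in some datasets whether the comparison can be made at all.

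**Working it through.** **The plan's own figure.** The only sample-size calculation concerns the primary outcome: a difference of 3.3 points, SD 6.3, and "power of 80% with an alpha 0.05". With n per arm = 2 × (1.960 + 0.842)² × (6.3/3.3)², the result is 57.2, which agrees with the stated 57 to within rounding up (power at 57 per arm is 79.9%). The SAP states no power, SD or effect for CRP, so no CRP figure can be reproduced.

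**Inputs for CRP.**
- From the SAP: two-sided alpha 0.05; 57 per arm (section 2.9), or 62 per arm (the Table 1 shell's 124 divided by 2); covariates baseline value and hospital.
- Assumed: CRP lognormal with median 1.5 mg/L; SD of log CRP 0.8, 1.0 or 1.2; correlation between baseline and 6 months 0.4, 0.6 or 0.7; a Shapiro-Wilk test at 5% as the residual check.

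**Effect size.** The treatment effect was set for about 80% power on the log scale:

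log ratio = −(1.960 + 0.842) × SD × √(1 − r²) × √(2/n)

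For SD 1.0, r 0.6 and n 57 this is −2.802 × 1.0 × 0.8 × 0.187 = −0.42, a CRP ratio of 0.657.

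**Power, 1,500 simulated trials per scenario (57 or 62 per arm, all three correlations).**

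| SD of log CRP | Raw-scale ANCOVA | Log-scale ANCOVA | Gap (points) |
|---|---|---|---|
| 0.8 | 60–65% | 79% | 14–19 |
| 1.0 | 52–58% | 78–81% | 21–29 |
| 1.2 | 43–48% | 77–80% | 30–36 |

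The gap depends on the effect. At 57 per arm and r 0.6, for SD 0.8, 1.0 and 1.2 in turn:
- ratio 0.9: 11.9 against 15.1%, 7.5 against 10.9%, 5.7 against 8.3%, so about 3 points;
- ratio 0.7: 67.5 against 84.3%, 41.6 against 65.5%, 26.9 against 50.7%, so 17 to 24 points.

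**What the written rule delivers.** Raw residuals failed the check in at least 99.7% of trials. With log as the transformation, power was 77–81%, the same as a pre-specified log ANCOVA, so the loss was about 0. That comparison scores the log ANCOVA even in trials where its residuals also fail.

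**How often the fallback is reached.** Log residuals failed in about 4–6% of trials, which is simply the error rate of the check when CRP is exactly lognormal. With departures from that shape (all assumed values), the failure rate was:
- 39% with 5% infection-type spikes;
- 63% with a detection floor at 0.6 mg/L;
- 94% with both.

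The floor is a demanding case. With median 1.5 and log SD 1.0 it puts Φ(ln(0.6/1.5)) = Φ(−0.92), about 18% of values, at the limit. Had a square root been chosen, its residuals would fail in 87–99% of trials (log SD 0.9–1.1, r 0.5–0.7, 50–62 per arm).

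**Type I error** was about 5% on both the raw and the log scale under lognormal CRP.

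**The case against.** The strongest reply is that section 4.5 does not end on the raw scale. A reader might infer that CRP is simply compared in mg/L and that the power in the table's last column is lost. The text does not support that. Skewed CRP almost always fails the check, the rule then calls for a transformation, and with log the loss is about 0. This part of the reply stands, so the power figure is conditional on the check being skipped, the skewness being accepted, or an unsuitable transformation being chosen.

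A reader might also infer that CRP will usually end in the mixed model. That does not follow either. No square root is mentioned in the SAP, log is the natural choice given Figure 1, and after log the fallback is rare if CRP is close to lognormal. How rare depends on outliers and detection-limit values, about which the SAP says nothing.

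Three further replies have some force:
- **Figure 1 is not a contradiction.** It gives the form of a predictor in a cited model and does not fix the scale of an outcome. That is correct. It shows only that the log scale is already in use.
- **The mixed-model sentence is written for the primary outcome.** True, and the random intercept for group is a general weakness. But section 4.5 gives no other fallback, and its rule covers the ANCOVAs in general.
- **Section 1 promises separate plans for secondary outcomes.** Sections 2.8 and 4.5 nevertheless set the CRP test here, so the promise does not remove the problem.

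**Conclusion.** The concern holds in limited form. The CRP scale is left to an unnamed, data-driven transformation after a check that skewed CRP will almost always fail. The fallback behind it cannot give the between-group CRP comparison that section 2.8 promises.

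The 14 to 36 points are the price of staying on the raw scale for effects detectable with about 80% power on the log scale. They are not the expected loss under the plan as written. They rest on assumed lognormality, log SD and correlation, and the fallback rates rest on an assumed check, spikes and floor.

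Nor do the results support reading the CRP test as invalid: the simulations show no inflation of false positives on either scale. Since CRP is also a secondary outcome with no power target, severity is minor.

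**What to change.** In section 4.5, take CRP out of the shared ANCOVA sentence and state that:
- log CRP at 6 months is analysed by ANCOVA with log baseline CRP, hospital and group;
- the result is reported as the ratio of geometric means with its 95% confidence interval;
- the generic transformation and mixed-model steps do not apply to CRP.

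The last item matters because the log model should stand even if a residual test rejects. Type I error stayed near 5% on the raw scale, where that test fails almost every time.

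The cost is one sentence, plus a CRP row in Table 2 labelled as a ratio. The downside is that the effect is no longer in mg/L. Non-detectable values need a positive substitute, but the log term in Figure 1 already requires one, and the same rule can serve both.

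### Change in medication use is promised as a between-group comparison, but the planned chi-square test names no time point and uses neither baseline use nor hospital

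*SAP*

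**What the plan says.** SAP Section 2.8 lists this among the secondary outcomes: "change in proportion of individuals using lipid lowering agents, antiplatelet or anticoagulant agents, or blood pressure lowering agents will be presented and compared between groups". The method is in Section 4.5: "Chi-Square tests will be used for the analysis of medication use as this is presented as dichotomous data". Two further sentences complete it: "The 95% CI will be presented for the difference in proportions" and "If expected cell frequencies are less than 5, Fisher's exact tests will be used". None of these states whether the tested variable is use at 6 months, stopping, starting or any change.

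Just before this, Section 4.5 says of LDL, body weight, CRP and systolic blood pressure that "similar ANCOVAs will be performed with adjustment for study site and baseline values". Section 2.4 says that "Allocation was stratified by hospital". Section 2.5 says that measurements were repeated at 3, 6 and 12 months and that the primary results use only the 6-month values. Six months is therefore the natural reading for medication too, but Section 4.5 does not say so. The shell of Table 2 in Section 5 has no medication row, so it does not settle the question.

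**The concern.** The endpoint concerns change, while the stated test is an unadjusted comparison of use. Use of long-term cardiovascular drugs is likely to be strongly correlated within a patient over six months. A 2x2 test on 6-month use then largely reflects who was already on treatment at entry, and the paired baseline value that would remove this variation is left out. The only reason given for treating medication differently from the continuous outcomes is that it is dichotomous, which is no reason to drop baseline use or the stratification factor.

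The comparison also bears on how the main result is read. Under Section 2.7, the 6-month risk is computed from baseline risk and the changes in LDL-cholesterol and systolic blood pressure, and two of the three drug classes act on these. The trial is unblinded (Section 2.4). A reader will look at the medication comparison to judge whether drug changes could explain a risk difference, and may take a non-significant result from an imprecise test as reassurance.

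**Working it through.** **Inputs from the SAP.** Total N is 124 in the Table 1 shell, and "Patients were randomly assigned in a 1:1 ratio to usual care or the intervention group", so about 62 per arm. Tests are two-sided at 0.05 (Section 4.1). The SAP's only power statement is for the primary outcome: 2 × (1.960 + 0.842)² × (6.3/3.3)² = 57.2 per arm, against 57 stated. That figure is not in dispute. For medication use there is no stated figure to reproduce.

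**Assumed inputs.** Baseline prevalence p, switching rates, and the correlation φ between baseline and 6-month use. The SAP gives none of these, so ranges are shown.

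**Step 1: ratio of standard errors with no effect.** For the unadjusted 6-month difference relative to the baseline-adjusted one, the ratio is 1/√(1 − φ²).

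| φ | ratio |
|---|---|
| 0.5 | 1.15 |
| 0.7 | 1.40 |
| 0.8 | 1.67 |
| 0.9 | 2.29 |
| 0.95 | 3.20 |

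**Step 2: from switching to φ.** With stable prevalence p and a fraction s of all patients switching, φ = 1 − (s/2)/(p(1 − p)). Take p = 0.80, so p(1 − p) = 0.16:

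- s = 0.05: φ = 1 − 0.025/0.16 = 0.84 and the ratio is 1.86. The standard errors are √(2 × 0.16/62) = 0.072 unadjusted and 0.072/1.86 = 0.039 adjusted.
- s = 0.10: φ = 0.69, ratio 1.38.
- s = 0.02: φ = 0.94, ratio 2.87.

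**Step 3: power in one example.** Assume p = 0.80, 3% against 15% of users stopping, and 5% of non-users starting in both arms.

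- Use at 6 months is 0.80 × 0.97 + 0.20 × 0.05 = 0.786 in one arm and 0.80 × 0.85 + 0.20 × 0.05 = 0.690 in the other. The difference is 0.096.
- Unadjusted: SE = √((0.786 × 0.214 + 0.690 × 0.310)/62) = 0.0785. Then 0.096/0.0785 = 1.22, and power is Φ(1.22 − 1.96), about 23%.
- Adjusted for baseline use: the variances within baseline groups sum to (0.80 × 0.97 × 0.03 + 0.20 × 0.05 × 0.95) + (0.80 × 0.85 × 0.15 + 0.20 × 0.05 × 0.95) = 0.144. A common baseline slope adds about 2 × 0.06² × 0.16 = 0.001. SE = √(0.145/62) = 0.048. Then 0.096/0.048 is about 2.0, and power is about 50%.
- The SE ratio here is 0.0785/0.048, about 1.6. The gain is smaller when there is an effect than when there is none.

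**Step 4: check by simulation.** At 62 per arm, 8,000 trials per setting, the chi-square test was compared with a linear model on arm, baseline use and hospital with robust standard errors.

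- No effect, p = 0.80, s = 0.05: the SD of the estimate was 0.072 against 0.039.
- No effect, all settings (p from 0.70 to 0.90): chi-square rejected in 4.1% to 5.3% of trials, so type I error is kept.
- No effect, p = 0.80: the unadjusted estimate correlated 0.68 to 0.85 with the chance baseline difference between arms.
- Stopping raised by 12 percentage points in one arm, p = 0.80, s = 0.05: the 6-month difference, the adjusted difference and the difference in change averaged −0.096, −0.097 and −0.096. Power was 24% against 45%. This setting has more starting (0.025/0.20 = 12.5% of non-users) than Step 3, hence the smaller gain.

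**The case against.** Chi-square or Fisher is conventional for a binary secondary outcome. Several stronger readings that a reader might infer are not supported.

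- **That the test does not address change, or is invalid.** Under randomisation the expected baseline difference is zero, so the 6-month difference has the same expectation as the difference in change, and type I error is kept. The cost is precision and exposure to chance imbalance.
- **That the test is certainly applied to 6-month use.** Section 4.5 does not say so. A chi-square on stopping or on any change would also fit the wording of Section 2.8. Simulation of the Step 3 setting gave power of 47% and 45% for these, close to the 50% of the adjusted model. This weakens the efficiency argument but not the point about specification: the variable is undefined, and an any-change variable would merge starters and stoppers, who move in opposite directions.
- **That the standard error is at most twice as large as needed.** A ratio of 2 requires φ of about 0.87. That is an assumption, not a bound.
- **That a chi-square cannot be combined with the pooling in Section 4.4.** That section imputes only data needed for the primary outcome. Medication use at 6 months is not an input to it: Section 2.7 uses anticoagulant use in the baseline score, and only LDL-cholesterol and systolic blood pressure for the change.
- **That the SAP treats medication change as the main rival explanation.** No section says this. It follows only from how the outcome is built.

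One further objection stands and shapes the remedy. A linear model with HC3 standard errors can fail with sparse data. At 95% use with 1% of users stopping and 5% of non-users starting, the standard error was undefined or zero in about 23% of simulated trials. The plan's Fisher fallback is worth keeping. Power also stays modest in the example even after adjustment.

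**Conclusion.** The point holds as a mismatch between endpoint and test, with an avoidable loss of precision. Section 2.8 promises a comparison of change, while Section 4.5 gives an unadjusted test of an undefined medication variable and departs from its own treatment of the continuous outcomes. If the test is applied to 6-month use, its standard error is about 1.15 to 2.3 times that of a baseline-adjusted analysis for an assumed φ of 0.5 to 0.9. In the worked example, power is about 23% against 50%. These sizes rest on assumed prevalence and switching, and on 62 per arm from the table shell. The gain comes almost wholly from baseline use. The reason for adding hospital is consistency with the stratified design and with the other outcomes. This is a secondary outcome and the primary analysis is unaffected.

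**What to change.** In Section 4.5:

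- State that the medication outcome is use at 6 months (yes/no) for each drug class.
- Estimate the between-group difference in proportions with 95% CI from a model with arm, baseline use and hospital. Either a linear model with robust standard errors or logistic regression with a standardised risk difference will serve; name one in advance.
- Keep raw n (%) per arm at baseline and 6 months as description, and add medication rows to the table shells.
- Keep Fisher's exact test as the fallback when too few patients switch for the model to be estimable, and define that condition beforehand.

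The cost is a few lines of SAP text and one model per drug class, on data already planned for collection. The small downside is slightly more analysis work and a model-based estimate for a binary secondary outcome.
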